4.5.3.3 Physical examination

A physical examination will be performed at screening, weekly up to and including week 4, week 5, week 8, and every 8 weeks thereafter. Details will be recorded in the pCRF.

4.5.4 Other safety measurements and variables

4.5.4.1 Pregnancy test

A pregnancy test (urine or serum) will be performed at screening, prior to starting treatment, and every 8 weeks relative to first dose with AZD8330 for female pre-menopausal patients.

4.5.4.2 MUGA scan/Echocardiogram

A MUGA and/or Echocardiogram will be conducted at screening, week 3 and week 5 (+/- 1 week). In addition, MUGA or Echocardiogram scans are required should signs of congestive heart failure occur at any time.

The modality of the cardiac function assessments must be consistent within patient, ie, if echocardiogram is used for the screening assessment then echocardiogram should also be used for subsequent scans if required.

4.5.4.3 BNP or NT-proBNP

Either BNP or NT-proBNP will be tested locally according to local practice at baseline (Visit 2) prior to initiation of treatment and thereafter at the same time as safety labs (see [Table 1](#)). In addition an unscheduled sample should be taken if there are any signs of congestive heart failure or dyspnoea.

The modality of these blood assessments must be consistent within patient, ie, if BNP is used for the screening assessment then BNP should also be used for subsequent assessments.

4.5.4.4 Troponin T (or Troponin I)

Troponin T (or Troponin I) will be tested at baseline (Visit 2) prior to initiation of treatment and thereafter at the same time as other safety labs (see [Table 1](#)) as part of the clinical chemistry sample. In addition an unscheduled sample for Troponin T (or Troponin I) analysis should be taken if there are any signs of cardiac adverse events.

4.5.4.5 Coagulation screen

APTT, PT and TT will be tested at baseline (Visit 2) prior to initiation of treatment and thereafter at the same time as other safety labs (see [Table 1](#)). In addition an unscheduled

coagulation screen including APTT, PT, TT, fibrinogen and d-dimer should be performed if there are any signs of bleeding adverse events.

4.5.4.6 O₂ saturation

A baseline measurement of oxygen saturation, performed by pulse oximetry will be recorded on Day 1 prior to dosing, at every vital sign assessment and as indicated as part of the routine management of patient on the occurrence of AEs eg, specific cardiac or respiratory symptoms. If there is a clinically significant drop in O₂ saturation this event should be followed up with full pulmonary function tests and HRCT scan of the chest if clinically indicated.

4.5.4.7 Chest X-ray

A chest X-ray will be performed at baseline and also in cases of dyspnoea and pulmonary oedema in addition to other assessments as per local standard practice. Results must be recorded in the pCRF.

Chest X-rays will be repeated as clinically indicated as part of the routine management of the patient on the occurrence of AEs.

4.5.4.8 Ophthalmological examination

A complete ophthalmologic examination including a slit-lamp examination must be performed within 2 weeks prior to first dose, and at week 5 (+/- 1 week), and if a patient experiences a visual disturbance AE. Results must be recorded in the pCRF.

4.6 Volume of blood sampling and handling of biological samples

The total volume of blood that will be drawn from each patient in this study, during their initial 35 days treatment period, is as follows:

Part A

Table 3 Part A Volume of blood to be drawn from each patient

Assessment	Sample volume (mL)	No. of samples	Total volume (mL)	
Pharmacodynamic	4	6	24	
Pharmacokinetic	2	32	64	
Safety	Clinical chemistry	6	30	
	BNP or NT-pro BNP	6	36	
	Haematology	2.6	6	15.6
	Coagulation	2.7	6	16.2
Optional host genetics	9	1	9	
Total			194.8	

The total volumes of blood given in [Table 3](#) is based upon a 35 days treatment period (including samples taken at the withdrawal visit). At each visit on treatment after this a further 16.3 mL (approximately) of blood will be taken for haematology, coagulation and clinical chemistry (including BNP). Clinical chemistry (including BNP, and Troponin T (or Troponin I)), coagulation and haematology samples are analysed locally, therefore volumes may vary according to local practice, and at some sites additional blood volume may be required for the Troponin T (or Troponin I) sample (approximately 2.7 mL per sample).

Table 4 – no longer applicable.

4.6.1 Analysis of biological samples

4.6.1.1 Clinical chemistry samples

All clinical chemistry samples will be analysed by the local laboratory. The analyte stability limits defined by the local laboratory will be applied to all analyses performed for this study. Samples that fall outside these stability limits should not be analysed. Analytical data will not be reported if found to have been derived from a sample that fell outside these stability limits.

4.6.1.2 Pharmacokinetic samples

The long-term stability of the analyte(s) should be documented in method validation produced by the AstraZeneca appointed CRO. Results from analyses of samples stored longer than the time period for which stability has been demonstrated should not be reported unless complementary analyte(s) stability data is acquired and appended to the relevant method validation report.

4.7 Genetic measurements and co-variables

See [Appendix D](#) and Laboratory Handbook for Investigators for details of optional blood sample collection for host genetic analysis of the study. The results of the genetic analysis will not be reported as part of the clinical study report for the study.

5. DATA MANAGEMENT

5.1 pCRF Data

Paper CRFs (pCRFs) will be provided for the recording of data not captured electronically. The pCRF will be in triplicate with carbonless paper. Data should be recorded legibly onto the forms in black ballpoint. If any data are not available, omissions will be indicated on the record forms. Corrections should be made legibly and initialled. Correction fluid or covering labels must not be used.

The AstraZeneca Monitor will check data at the monitoring visits at the investigational site. The pCRF must be signed by the Investigator to confirm that they have been checked for

accuracy and completeness; this signature should include review of all the latest test results. The top original and first copy of the completed form will be collected. The top original will be sent to data management personnel. The remaining copies will be retained at the study centre unless the Marketing Company (MC) is required to retain a copy of the CRF in their local files. In this case, the monitor will also collect the 1st copy of the CRF and retain it at the MC according to local guidance.

Data from the completed pCRFs will be entered onto AstraZeneca's clinical study database and undergo validation checks for correctness and completeness under the direction of the Study Co-ordinator.

Any data queries arising from in-house validation checks, such as missing, impossible or inconsistent recordings in the pCRFs will be detailed on data query forms (DQFs) that will be forwarded to the investigator, via the monitor. After resolution of the query on the DQF, it should be photocopied twice. The original DQF will be returned to AstraZeneca. The monitor will retain a photocopy and another photocopy will be retained at the investigational site.

All data captured electronically eg, ECG results, PK results, will be transferred directly to the appropriate database. Validation and quality control of this is the responsibility of the provider.

5.2 Dose Escalation Decision Data

Dose escalation decisions will be based upon unvalidated data.

5.3 Pharmacokinetic and Pharmacodynamic Data

The pharmacokinetic and pharmacodynamic data will be fully validated before being sent to the data management technology (DMT) programmer. The data will be provided in a format agreed up front with the DMT programmer (eg, EXCEL spreadsheet).

5.4 Biomarker analysis of tumour material (Not applicable)

No longer applicable.

5.5 Pharmacogenetic Data (host)

The samples and data for host genetic analysis in this study will be coded. The samples will be labelled with a clinical study patient number that can be traced or linked back to the patient only by the investigator. The samples and data will not carry a personal identifier. The date of sample collection and confirmation that the patient has signed the appropriate informed consent form will be recorded on a pCRF.

In the case of genetic data, only the date the patient gave consent to participation in the host genetic research, the date the tumour material and blood sample was taken from the patient will be recorded in the electronic pCRF and database.

The genetic data generated from the blood sample from this study will be stored in the AstraZeneca LIMS database or other appropriate system. This database is a secure database, which is separate from the database used for the main study. Some or all of the datasets from the main study may be duplicated within the AstraZeneca LIMS database/other appropriate system for exploratory genetic analysis.

5.6 Reporting of genetic data (host)

Results from any host genetic research performed will be reported separately from the clinical study report. AstraZeneca will not provide individual genetic results to patients, their family members, any insurance company, an employer, clinical study investigator, general physician or any other third party, unless required to do so by law. The patient's DNA will not be used for any purpose other than those described in the study protocol.

Individual patients will not be identified in any report or publication resulting from this work. The data and results of this study may be reviewed with collaborators and published, but neither the patient's name nor any other personal identifiers will appear in any publication or report.

6. STATISTICAL METHODS AND DETERMINATION OF SAMPLE SIZE

6.1 Statistical evaluation – general aspects

The Statistical Analysis Plan (SAP) will not be prepared for this study since the detail of all planned analyses are included in this protocol.

6.2 Description of outcome variables in relation to objectives and hypotheses

The primary objective of this study is to assess the safety and tolerability of AZD8330 in patients with advanced malignancies. This objective will be assessed by AEs, clinical chemistry, haematology, urinalysis, vital signs, MUGA scan/Echocardiogram, ECGs Ophthalmologic examination, and O₂ saturation.

The secondary objective of determining the pharmacokinetics of AZD8330 and any known major metabolites following both single and multiple oral dosing of AZD8330 in patients with advanced malignancies will be assessed by derivation of pharmacokinetic parameters for both AZD8330 and any known major metabolites, which may include include C_{max}, t_{max}, AUC, CL/F, and t_{1/2}.

The secondary objective of investigating the extent of pERK inhibition in PBMCs, will be assessed by the change in pERK in PBMCs at 30 minutes, 1 hour 30 minutes, 4, 8 and 24 hours post-dose compared to pre-dose levels.

If the data are suitable, potential relationships between plasma AZD8330 and any known major metabolites concentrations/exposure and changes in safety parameters will be investigated using a graphical approach and/or appropriate PK/pharmacodynamic modelling techniques.

6.3 Description of analysis sets

Population	Definition
Evaluable for safety	This will include all patients who received at least one dose of study medication ^a .
Evaluable for PK analysis	This is a subset of the safety population that includes all patients who provide AZD8330 concentration data and/or any known major metabolites concentration-time data.
Evaluable for Dose Escalation Evaluation (Part A)	This is a subset of the safety population that includes all Part A patients who have had all PK assessments (Day 1) performed, and who have sufficient safety evaluations performed during 35 days dose period from first dose at the discretion of the Safety Review Committee, or have suffered a DLT.

a If a patient discontinues study medication and starts another anti-cancer therapy, all data after 30-day follow-up period for that patient will be excluded from the assessment of safety.

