3.1.4 Part A: Dose Escalation Phase

Six patients will be recruited to the first cohort to receive a single 0.5 mg dose of AZD8330 on Day 1, followed by continuous 0.5 mg once daily dosing from Day 8. The starting dose administered was calculated based on preclinical toxicology results using the FDA starting dose calculation for oncology compounds. If this dose is tolerated then a further six patients will be recruited to a higher dose and dose escalation will continue until a non-tolerated dose is reached.

Replacement patients may be enrolled until the minimum required number of evaluable patients are available for assessments. Reasons for patient withdrawal will be given due consideration when enrolling replacement patients.

No more than 3 patients will start dosing in the first seven days of a cohort opening, after which a further 3 patients may start dosing. See Section 3.2.1 for further rationale on the starting dose and study design.

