3.1.4.1 Dose Escalation Criteria to Maximum Tolerated Dose

Prior to each dose escalation in Part A, the Safety Review Committee (see Section 6.8) will meet to review the available safety and PK data. The dose escalation decision will be formally minuted and the minutes distributed to each site. Cohort dose escalation/de-escalation decisions in Part A, will be taken by the Safety Review Committee. The dose escalation/de-escalation decisions will be performed following review of available clinical data, the observed number of DLTs (see Section 3.1.4.2 for DLT definitions), PK data (C_{max} and AUC), and all safety assessments up to Day 35. Patients must have had sufficient safety evaluations performed during the 35 day dosing period, at the discretion of the Safety Review Committee. All dose escalation decisions by the Safety Review Committee will take into account the anticipated magnitude of plasma AZD8330 exposure in addition to the safety profile.

The decision criteria for dose escalation in any group of 6 to 9 patients are:

- For each group a Safety Review Committee will be held as soon as possible after 6 patients complete at least 35 days of treatment¹.
- The Safety Review Committee will define the dose for that group as a tolerated dose or a non-tolerated dose.
 - A non-tolerated dose is one where >25% of the patients experience a DLT. That is a dose where a dose limiting toxicity (DLT) is observed in $\geq 2/6$, $\geq 2/7$, $\geq 3/8$, or $\geq 3/9$ patients.
 - A tolerated dose is one where $\leq 25\%$ of the patients experience a DLT. That is, a dose where a DLT is observed in $\leq 1/6$, $\leq 1/7$, $\leq 2/8$, or $\leq 2/9$.
- If the dose is defined as tolerated, an increased dose will be investigated in another group of 6 to 9 patients.
- Recruitment to a group will be terminated if the number of DLTs observed in a group meets the above criteria for a non-tolerated dose before recruitment to that group is completed.
- No patients will be recruited to a cohort after the Safety Review Committee for that cohort has met and defined the dose as tolerated or non-tolerated.
- In the event that DLTs are observed in a group within 35 days of commencing treatment such that a dose initially considered tolerated by the Safety Review Committee becomes non-tolerated and dose escalation has already occurred:

- Recruitment to the escalated dose group will cease, and

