3.2 Rationale and risk/benefit assessment

3.2.1 Rationale for study design, doses and control groups

This study is designed to investigate the safety, tolerability and pharmacokinetic profiles of AZD8330. A dose of 0.5 mg is being proposed as the starting dose in the first-in-man study in advanced cancer patients. This is based on the FDA guidance for starting dose selection for cytotoxic agents in cancer patients, which recommends that a starting clinical dose for a 'first-in-humans' study should be either 1/10th of the severely toxic dose (STD₁₀) in rodent toxicity studies or 1/6th of the non-seriously toxic dose (NSTD) observed in non-rodent toxicity studies. Whilst a STD₁₀ was not established for AZD8330 in rodents, the high dose level of 3 µmol/kg/day (8.4 mg/m²) from the one month rat study has been used for this calculation. In dogs, the mid dose level of 0.15µmol/kg/day (1.4 mg/m²) from the one month study represents the NSTD. Following the FDA guidance, and using the conversion factors published on the FDA website ([FDA Guidance for Industry, July 2005](#)), the human equivalent dose (HED), derived from the rat data, was calculated to be 1.4 mg/day for a 60 kg man, whilst that derived from the dog study was calculated to be 0.4 mg/day. A compromise approach to initial dose selection has been proposed and a dose of 0.5 mg/day is deemed to be an acceptable starting dose for the initial trial in patients.

Each dose escalation decision will be made after a cohort of patients have either completed a 35 day dose period on study or have experienced a DLT, at the discretion of the Safety Review Committee. Prompt pharmacokinetic analysis of samples from Day 1 will guide each dose escalation decision between cohorts, along with the review of all the safety and tolerability data. Cohorts of six patients will be recruited throughout the study to allow better characterisation of the PK and pharmacodynamic effects of AZD8330, and because when the underlying DLT rate in the population is unknown there is a lower probability of escalating from what would be a tolerated dose in the population to a non-tolerated dose using a cohort of 6 patients than with the more traditional 3 + 3 study design. To ensure there is not a consistently acute and severe tolerability issue at any new cohort, no more than 3 patients will be dosed in a cohort within the first 7 days.

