4.3.1 Collection of biological samples

Analysis of plasma samples for the determination of AZD8330 and any known major metabolite will be the responsibility of Drug Metabolism and Pharmacokinetic Department, Alderley Park, AstraZeneca, UK.

Venous blood samples (2 mL) will be collected to provide plasma for analysis.

Labels for tubes are unique, enabling identification of the study, compound to be analysed, patient/centre number, visit number and protocol scheduled time point.

Samples will be shipped initially to the coordinating laboratory, and subsequently sent for analysis to a referral laboratory. A sample inventory must accompany each shipment of samples.

Details of sample collection, storage and shipment will be provided in the Laboratory Manual for Investigators.

Although every attempt should be made to collect all samples as protocolled, it is accepted that this will not always be possible and therefore it is essential that the actual time and date of collection of each blood sample (whether collected as protocolled or not) is recorded on the pCRF.

4.3.2 Drug concentration measurements, and derivation or calculation of pharmacokinetic parameters

Blood samples (2 mL) for determination of plasma AZD8330 will be taken at the times specified in the Study Plan [Table 1](#) and Section 4.3. The actual timings may change depending on the emerging data from this study. Other metabolites may be analysed from the same blood sample if warranted. PK samples will not exceed the volumes provided in [Table 3](#). The date and time of collection will be recorded. Further details of sample collection and shipment will be provided in the Laboratory Manual for Investigators.

The pharmacokinetic analyses will be undertaken for both plasma AZD8330 and any known major metabolite by (or on behalf of) the Clinical Pharmacology Group, AstraZeneca (Alderley Park).

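### The dose-escalation set in section 6.3 requires complete Day 1 PK of DLT-free patients but not of DLT patients; if it is the denominator of the >25% rule, missed PK biases the decision modestly towards non-tolerated

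*Protocol*

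**What the plan says.** Three places in the protocol describe who counts towards an escalation decision.

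- **Section 6.3**, the set evaluable for dose escalation: "all Part A patients who have had all PK assessments (Day 1) performed, and who have sufficient safety evaluations" over the 35-day period, with the closing words "at the discretion of the Safety Review Committee, or have suffered a DLT".
- **Section 3.1.4.1**, the decision rule: "Patients must have had sufficient safety evaluations performed during the 35 day dosing period, at the discretion of the Safety Review Committee". PK completeness is not mentioned as a condition on the patient.
- **Section 3.2.1**, the rationale: the decision follows once patients "have either completed a 35 day dose period on study or have experienced a DLT". Again there is no PK-completeness condition.

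The rule is introduced by "The decision criteria for dose escalation in any group of 6 to 9 patients are", and its threshold is: "A non-tolerated dose is one where >25% of the patients experience a DLT". The listed cut-offs for non-tolerated are 2/6, 2/7, 3/8 and 3/9.

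Section 4.3 schedules 11 PK samples on Day 1, the last at 24 hours. Section 4.3.1 says: "Although every attempt should be made to collect all samples as protocolled, it is accepted that this will not always be possible". Section 3.1.4 adds: "Replacement patients may be enrolled until the minimum required number of evaluable patients are available for assessments". Section 6.1 states that no separate SAP will be prepared.

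**The concern.** Inclusion in the 6.3 set depends on the outcome being counted. Read as (complete PK and sufficient safety) or DLT, the definition admits every DLT patient and screens only the DLT-free ones on PK. A missed blood draw says nothing about tolerability, yet it can only shrink the DLT-free part of the denominator. The discretion given to the Safety Review Committee attaches to the adequacy of the safety evaluations, not to the PK condition, so it does not repair this. Replacement restores the number of evaluable patients but not the balance, because every patient lost for PK is DLT-free.

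A non-tolerated classification stops escalation, and the MTD is defined from it. An avoidable shift in that classification therefore reaches the study's dose-finding result. The direction is always towards a lower dose. A PK condition can also call for replacement patients whom the safety question does not need.

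**Working it through.** **Inputs.** From the protocol: cohorts of 6 to 9, the >25% threshold, and 11 Day 1 PK samples. Assumed, because the protocol gives no rate: a share m of DLT-free patients with incomplete Day 1 PK (5% to 20%), independent of other patients, and a true DLT rate p of 20% or 25%.

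**1. The plan's own cut-offs.** The smallest count r with r/n > 0.25 is:

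| n | non-tolerated from | share | largest tolerated | share |
|---|---|---|---|---|
| 6 | 2 | 33.3% | 1 | 16.7% |
| 7 | 2 | 28.6% | 1 | 14.3% |
| 8 | 3 | 37.5% | 2 | 25.0% |
| 9 | 3 | 33.3% | 2 | 22.2% |

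These agree with section 3.1.4.1.

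**2. Where the classification itself changes.** All combinations of treated, DLT and PK-incomplete patients that leave at least 6 evaluable were enumerated. Only these flip from tolerated to non-tolerated:

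- 8 treated, 2 DLTs (2/8 = 25.0%): one DLT-free patient dropped gives 2/7 = 28.6%; two dropped gives 2/6 = 33.3%.
- 9 treated, 2 DLTs (2/9 = 22.2%): two dropped gives 2/7; three dropped gives 2/6.

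With 6 or 7 treated there is no flip unless fewer than 6 remain evaluable. With no DLTs there is never an effect.

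**3. How often PK might be incomplete.** If completeness means all 11 samples, the share of patients missing at least one is 1 − (1 − s)^11 for a per-sample miss rate s. For s = 0.5%, 1% and 2% this gives 5.4%, 10.5% and 19.9%.

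**4. DLT share among evaluable patients.** P(DLT | evaluable) = p / [p + (1 − p)(1 − m)].

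- p = 25%, m = 10%: 0.25 / (0.25 + 0.75 × 0.9) = 0.25 / 0.925 = 27.0%.
- p = 25%, m = 20%: 0.25 / (0.25 + 0.75 × 0.8) = 0.25 / 0.85 = 29.4%.

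**5. Six evaluable patients, filled by replacement.** P(non-tolerated) = 1 − (1 − π)^6 − 6π(1 − π)^5, with π from step 4.

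| true p | m = 0 | m = 10% | m = 20% |
|---|---|---|---|
| 25% | 46.6% | 51.3% | 56.7% |
| 20% | 34.5% | 38.7% | 43.8% |

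**6. Eight or nine treated, no replacement, p = 20%.** The added probability is P(exactly 2 DLTs) times the probability that the required number of DLT-free patients lack PK, keeping at least 6 evaluable. For 8 treated, P(2 DLTs) = 0.2936, and with m = 10% the chance that one or two of the six DLT-free patients are dropped is 0.3543 + 0.0984 = 0.4527. The product is 13.3 points, which takes P(non-tolerated) from 20.3% to 33.6%. For m = 5% and 20% the totals are 28.0% and 39.1%. For 9 treated the additions are 1.3, 4.4 and 11.8 points for m = 5%, 10% and 20%. These figures ignore the rule that closes recruitment once the non-tolerated count is met, so they overstate how often a group would get there.

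**The case against.** The strongest reply is that the denominator is inferred. Section 3.1.4.1 speaks of groups of 6 to 9 patients and does not cite the 6.3 set. That set could serve only to define the evaluable minimum for replacement in section 3.1.4 and the six evaluable patients at the MTD in section 6.5. The Safety Review Committee reviews all available data, and its guidelines are not shown. The safety requirement in 3.1.4.1 is also worded as necessary, not as sufficient. This stands: the documents do not prove that a DLT-free patient is struck from the fraction. But the set is titled for the dose-escalation evaluation, and no other section names a denominator.

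A reader might infer that one missed tube will exclude a patient and reverse a decision. That goes too far. Section 6.3 asks that all Day 1 PK assessments be performed; treating a single absent sample as failure is one interpretation. The flip needs exactly 2 DLTs among 8 or 9 treated. Planned cohorts are six, and two DLTs seen among the first 6 or 7 would normally close recruitment.

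A reader might also infer that the once-daily MTD already declared is in doubt. Section 1.1.3 reports 4 of 9 patients affected at 40 mg, which exceeds 25% with all nine counted. Dropping DLT-free patients could only raise that share. Any exposure lies in cohorts still to be run, such as twice-daily dosing.

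Nor is the PK condition pointless. Sections 3.1.4.1 and 3.2.1 make PK an input to escalation, and the PK set in 6.3 has no completeness condition, so simply deleting the phrase would leave no requirement for Day 1 profiles.

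Finally, a set defined as sufficient safety evaluation or a DLT still always admits DLT patients. True, but incomplete follow-up leaves DLT status unknown, whereas missing PK does not.

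The sentence in 6.3 can also be parsed as complete PK together with either safety evaluations or a DLT. The comma and section 3.2.1 favour the reading used here. The alternative would discard an observed DLT for missing PK, which also needs correcting.

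**Conclusion.** The point holds in a limited form. Section 6.3 treats DLT and DLT-free patients differently on a condition unrelated to tolerability, and it does not match 3.1.4.1 or 3.2.1. If 6.3 governs the >25% rule, the bias is one-way, towards calling a dose non-tolerated. At a true DLT rate of 25%, which is the rule's own boundary, it adds about 5 points at 10% incomplete PK and 10 points at 20% for six evaluable patients reached by replacement. A changed classification of a given group is confined to 2 DLTs in 8 or 9 treated.

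The sizes rest on assumed missing-PK rates, on independence between patients, and on 6.3 being the denominator. The inconsistency between the sections rests on none of these. The documents do not support saying that decisions already taken were wrong, or that the committee must drop a patient for one missed sample.

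**What to change.** In section 6.3, define DLT evaluability as having had a DLT, or having sufficient safety evaluations over the 35-day window as judged by the Safety Review Committee, with no PK condition. State that this set is the denominator of the >25% rule, and make 3.1.4.1, 3.2.1 and 6.3 use the same definition.

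Keep the Day 1 PK requirement as a separate condition for the committee's PK review, and for PK replacement if that is wanted. State how complete the profile must be, because the current PK set does not.

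The cost is a few sentences. The cut-offs stay as they are: 2 DLTs in 8 remains 25.0% and 2 in 9 remains 22.2%, whatever PK is missed. The small downside is that some patients in the DLT denominator may lack a full Day 1 profile, which the separate PK condition addresses.
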